Refer to Section 6.1.1.2. Dosage, Preparation, and Administration for complete description of dupilumab and placebo for dupilumab for this study. Dupilumab will be administered SC in-clinic by trained clinical staff at least 30 minutes prior to the ingestion of the in-clinic milk OIT dose in order to allow for an accurate attribution of AE relatedness to study drug or milk. The administration of the loading dose of dupilumab will allow systemic concentrations to reach steady-state faster. Rapid attainment of target saturating concentrations may yield a rapid clinical response within 4-week period of dupilumab pre-treatment by suppressing Type 2 effector cell function, which is believed to be responsible for the allergic GI side effects of OIT. Dupilumab blockade of IL-4/IL-13 in AD, an immune-driven disease, reduced skin lesions and suppressed at 4 weeks the mRNA expression of genes related to T-cells, dendritic cells, eosinophils, inflammatory pathways, and Th2-inducing chemokines, whereas increases or insignificant decreases were observed with placebo. The correlation between these mechanistic changes and rapid improvement in clinical measures of disease activity, including Eczema Area and Severity Index (EASI) and Scoring Atopic Dermatitis (SCORAD) scores, support a milk protein OIT study design with only 4 weeks of dupilumab SC pre-treatment ([Hamilton 2014](#)). Rapid improvements in forced expiratory volume in 1 second (FEV1) and fractional exhaled nitric oxide have also been observed within 4 weeks in dupilumab studies in asthma ([Wenzel 2013](#), [Wenzel 2016](#)). The results in other indications suggest 4 weeks of dupilumab treatment significantly suppresses Type 2-mediated responses.

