2.3. Secondary Objectives

Clinical

- To assess the effect of dupilumab (compared to placebo) on tolerance of cumulative doses of ≥ 1040 mg and 4040 mg milk protein at week 18 DBPCFC
- To assess the effect of dupilumab (compared to placebo) on tolerance of cumulative doses of ≥ 1040 mg, ≥ 2040 mg, and 4040 mg milk protein at week 24 DBPCFC
- To compare levels of desensitization, defined as an increase in the cumulative tolerated protein dose (log transformed) of milk protein, from baseline to week 18 and baseline to week 24 DBPCFCs across treatment cohorts

Safety

- To compare the rates and severity of OIT-induced gastrointestinal symptoms in subjects receiving dupilumab compared to placebo.
- To compare the safety of each treatment cohort as measured by rate and severity of allergic and non-allergic AEs during respective study phases
- To compare rates of study completion among treatment cohorts

Exploratory and Mechanistic

[figure not shown]
- To explore the relationship between OIT-induced gastrointestinal symptoms and esophageal eosinophilia in subjects receiving dupilumab compared to placebo, if data is available
- To evaluate the immunological responses associated with OIT-induced AEs and successful desensitization

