3.5.2. Secondary Endpoints

Clinical Endpoints:

- Comparisons of each treatment group for the following:
 - Proportion of participants who tolerate at least 1040 mg cumulative milk protein during DBPCFC at week 18
 - Proportion of participants who tolerate 4040 mg cumulative milk protein during DBPCFC at week 18
 - Proportion of participants who tolerate at least 1040 mg cumulative milk protein during DBPCFC at week 24

- Proportion of participants who tolerate at least 2040 mg cumulative milk protein during DBPCFC at week 24
- Proportion of participants who tolerate 4040 mg cumulative milk protein during DBPCFC at week 24
- Change in the cumulative tolerated dose (CTD) of milk protein during DBPCFC from baseline to week 18 and baseline to week 24 across cohorts as pairwise comparisons of all treatment groups.
- Due to the positive skew for the distribution of the CTD, a log transformation will be applied to reduce the skewness.

Safety Endpoints:

- The rate and severity of OIT-induced gastrointestinal symptoms in subjects receiving dupilumab compared to placebo.
- Proportion of participants who have OIT-induced gastrointestinal symptoms, dupilumab compared to placebo
- The rate and severity of AEs, serious adverse events (SAEs), and safety events in each cohort
- Proportion of participants completing the study among cohorts

Exploratory and Mechanistic Endpoints:

- Change from baseline to week 24 in the log-transformed minimum concentration of milk protein which activates basophils, comparison between dupilumab and placebo
- Percent change from baseline to week 24 in milk-specific and total IgE and milk-specific and total IgG4, comparison between dupilumab and placebo
- Percent change from baseline to week 24 in milk skin prick test (SPT) response, comparison between dupilumab and placebo
- Proportion of subjects experiencing esophageal eosinophilia, dupilumab compared to placebo, if data is available

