6.3. Assessment of Participant Compliance with Investigational Agent

Participants (and families) will document daily dosing and any reactions from at-home dosing on Dosing & Symptom Diary Logs. For milk OIT-related symptoms, participants will be reminded to report itching of the tongue or mouth; tongue/mouth/throat pain; lip/tongue/throat swelling; stomach pain; nausea/vomiting; nasal itching or congestion; runny nose; and hives around the mouth or face. For specific symptoms related to the study injection, participants will be reminded to report injection site pain, redness, tenderness, and swelling. Parents or caregivers should fill out the diary daily for children less than 12 years old. Children 12 years old and above may fill out the diary themselves with parent or caregiver supervision. Monitoring of compliance will be performed by reviewing the participant's diary and monitoring and counting their returned, unused study product. Unused milk OIT doses will be brought back to the clinic with each visit and collected by study staff for reconciliation of remaining doses.

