11.2. Definitions

11.2.1. Adverse Event

Any untoward or unfavorable medical occurrence associated with the use of an intervention in humans, whether or not considered related to the intervention (see 21 CFR 312.32(a)). An AE can be any unfavorable and unintended sign, symptom, or disease temporally associated with the use of a drug, and does not imply any judgment about causality. An AE also includes any worsening (i.e. any clinically significant change in frequency and/or intensity) of a pre-existing condition that is temporally associated with the use of the study drug.

All symptoms or events that occur within two hours and that are expected according to the Investigator's Brochure (milk OIT), package insert (dupilumab), or protocol and related to administration of study drug or oral food challenge will be recorded as a dosing reaction, not an AE; however, episodes in response to home dosing that are Grade 3 or higher per CTCAE V5.0 criteria or that are classified as serious adverse events (SAEs) per **Section 11.2.4.** below, will be recorded on the AE/SAE case report form (CRF) as appropriate.

Any symptom or event that occurs more than two hours after study dosing will be recorded as an AE on the AE CRF but will not be identified as a dosing reaction.

For this study, an AE will include any untoward or unfavorable medical occurrence associated with:

Study therapy regimens:

Dupilumab/Placebo for Dupilumab
In-clinic OIT dosing
Home OIT Dosing

For the study-mandated procedures below, only the signs and symptoms listed under each procedure will be considered outside normal range and will be recorded as an AE. For all other study-mandated procedures, all AEs will be recorded.

Skin Prick Test

The following events related to SPT will be considered AEs if they occur within 48 hours of the SPT:

- Prolonged (>24 hours) pruritus at the SPT site
- Induration/swelling at the SPT site larger than 10 mm in diameter and lasting more than 24 hours
- Allergic or anaphylactic reaction that requires the use of rescue medications, detailed in **Section 7.2**

Blood Draw

The following events related to a blood draw procedure will be considered AEs:

- Syncope/vasovagal events within 30 minutes of the procedure
- Bleeding from the puncture site lasting more than 30 minutes
- Bruising at the puncture site >5 cm in diameter within 24 hours of procedure
- Erythema at the puncture site >5 cm in diameter within 24 hours of procedure

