11.2.2. Suspected Adverse Reaction

Any AE for which there is a reasonable possibility that the investigational drug (dupilumab, and/or milk OIT) caused the AE. For the purposes of safety reporting, 'reasonable possibility' means there is evidence to suggest a causal relationship between the drug and the AE. A suspected adverse reaction (SAR) implies a lesser degree of certainty about causality than an AE, which means any AE caused by a drug (21 CFR 312.32(a)).

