11.3.2. Attribution

The relationship, or attribution, of an AE to the study therapy regimen or study procedures will be determined by the investigator(s) based on all available information and recorded on the appropriate AE/SAE CRF. Final determination of attribution for safety reporting will be determined by the Sponsor.

Table 6. Attribution of Adverse Events

Category	Descriptor	Relationship (to Study Drug or Procedure)
UNRELATED CATEGORY	Not Related	The AE is clearly not related; there is insufficient evidence to suggest a causal relationship.
RELATED CATEGORIES	Possible	The AE has a reasonable possibility to be related; there is evidence to suggest a causal relationship.
	Definite	The AE is clearly related.

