13.6. Safety Analysis

13.6.1. Adverse Events

Definitions

For safety variables, 2 observation periods are defined:

- The pretreatment period is defined as the time from signing the ICF to before the first dose of study drug.
- The treatment period is defined as the day from first dose of study drug to the end of the study.

Treatment-emergent adverse events are defined as those that are not present at baseline or represent the exacerbation of a pre-existing condition during the on-treatment period.

Analysis

All AEs reported in this study will be coded using the currently available version of the CTCAE. Coding will be to lowest level terms. The verbatim text, the preferred term (PT), and the primary system organ class (SOC) will be listed.

Summaries of all AEs by treatment group will include:

- The number and percentage of subjects with at least 1 AE by SOC and PT
- AEs by severity, presented by SOC and PT
- AEs by relationship to treatment (related, not related), presented by SOC and PT
- Treatment-emergent AESIs (defined with a PT or a prespecified grouping)

Deaths and other SAEs, as well as AEs leading to permanent treatment discontinuation, will be listed and summarized by treatment group.

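### Section 13.6.1 tabulates related AEs against one undivided treatment, so no listed table isolates the milk-OIT-related events that the safety objectives name

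*Combined protocol and SAP*

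**What the plan says.** Section 13.6.1 lists the AE summaries to be produced by treatment group. The only one concerned with causality is "AEs by relationship to treatment (related, not related), presented by SOC and PT". It does not say whether treatment means milk OIT, the injection, or either.

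The sections that feed this table also join the two agents. Section 11.2.2 defines a suspected adverse reaction as "Any AE for which there is a reasonable possibility that the investigational drug (dupilumab, and/or milk OIT) caused the AE". Section 11.3.2 has the investigator attribute each AE to the study therapy regimen or to study procedures, and does not ask for a separate judgement on each product.

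Other sections assume that the two can be told apart. Section 1.2.3.1 sets the interval between injection and in-clinic milk dose "in order to allow for an accurate attribution of AE relatedness to study drug or milk". The sample SAE form in Appendix 3 has two study-medication boxes, each with its own relatedness choices. Section 6.3 asks participants to report milk-related and injection-related symptoms as separate lists. The hypothesis in section 2.1 concerns AEs associated with milk OIT. A safety objective in section 2.3 is "To compare the rates and severity of OIT-induced gastrointestinal symptoms in subjects receiving dupilumab compared to placebo", and section 3.5.2 turns it into endpoints, the first being "The rate and severity of OIT-induced gastrointestinal symptoms in subjects receiving dupilumab compared to placebo".

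Section 11.2.1 also limits what reaches the AE tables. Symptoms within two hours that are expected and "related to administration of study drug or oral food challenge will be recorded as a dosing reaction, not an AE"; the exceptions are home-dosing episodes that are Grade 3 or higher, or that are serious.

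**The concern.** The two agents are expected to move AE frequency in opposite directions. Dupilumab is hypothesised to reduce milk reactions, while section 6.4 refers to a higher incidence of local injection-site reactions with dupilumab. A relatedness classification that does not name the agent mixes the two signals wherever they share a term or a total.

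At stake is whether the trial can report on its own OIT-safety objective. OIT-induced is not defined anywhere, and no table listed in section 13.6.1 is restricted to events judged related to milk. If attribution to each product is not recorded prospectively by blinded investigators, it cannot be reliably rebuilt after unblinding.

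**Working it through.** The plan gives no figure on this point, so there is none to reproduce. The check has two parts.

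**1. Which rows are ambiguous.** Setting the risk lists side by side:

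| Term | Listed for dupilumab | Listed for milk OIT |
|---|---|---|
| Urticaria | 5.2 | 5.3 |
| Rash | 5.2 | 1.1 |
| Pruritus (skin or eye) | 5.2 | 1.1, 5.3 |
| Anaphylaxis | 5.2, 11.2.5 | 5.3, 11.2.5 |
| Diarrhea | 5.2 | 1.1, 11.2.5 |
| Injection-site reaction | 5.2, 6.4 | not listed |

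A related count in any of the first five rows cannot be assigned to an agent. Diarrhea matters most, because it belongs to the gastrointestinal endpoint itself. The injection-site row is unambiguous.

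**2. How far an overall related-AE count would be diluted.** Section 13.6.1 does not list such a line, so this is an illustration.

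Inputs:
- OIT-related AEs under placebo: 95%, the upper figure in section 1.1.
- OIT-related AEs under dupilumab: 75%, assumed.
- Injection-related AEs: 5% to 20% under placebo and 10% to 40% under dupilumab, assumed; the documents give no rate by arm.
- 58 per arm (section 13.2); the two kinds of event assumed independent.

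Formula: P(any related) = 1 − (1 − OIT)(1 − injection).

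For injection rates of 5% and 15%:
- placebo: 1 − 0.05 × 0.95 = 0.9525
- dupilumab: 1 − 0.25 × 0.85 = 0.7875
- difference: 16.5 points, against 20 for OIT-related events alone.

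The last column is the power of a two-sided 5% chi-square test, by enumeration. It is only a yardstick, since section 13.6.1 plans no AE test.

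| Injection rate, placebo / dupilumab | Any related, placebo / dupilumab | Difference (points) | Power |
|---|---|---|---|
| none (OIT-related only) | 95.0% / 75.0% | 20.0 | 89% |
| 5% / 10% | 95.25% / 77.5% | 17.75 | 84% |
| 5% / 15% | 95.25% / 78.75% | 16.5 | 79% |
| 5% / 20% | 95.25% / 80.0% | 15.25 | 74% |
| 10% / 40% | 95.5% / 85.0% | 10.5 | 50% |
| 20% / 40% | 96.0% / 85.0% | 11.0 | 55% |

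The difference vanishes when the dupilumab injection rate equals 1 − (0.05)(1 − placebo injection rate)/0.25. That is 80% if the placebo rate is 0, and 84% if it is 20%.

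**The case against.** The strongest reply is that the SOC/PT layout already separates most of what matters. An injection-site reaction or conjunctivitis sits on its own row by arm, and so do vomiting and abdominal pain. This stands for those terms. It does not help with the shared terms above, nor with an OIT-related total.

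A second reply is that the protocol handles OIT events elsewhere: gastrointestinal symptoms are separate endpoints, AESIs are listed by product in section 11.2.5, and the sample SAE form takes two attributions. This is partly right. But the endpoints rest on an undefined term, life-threatening anaphylactic reactions appear on both AESI lists, and the SAE form covers only serious events and others reported through it. Section 13.5.2 promises descriptive analysis of all secondary endpoints without saying which events count as OIT-induced.

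A third is that section 13 is only the basis for a SAP to be finalised before database lock, where table shells would be set. That is fair for layout. It does not cover data capture: attribution by agent has to be on the AE form while events are being recorded. The routine AE form is not in the documents, so it may already carry both fields.

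Finally, AE summaries are descriptive, and section 13.5.4 controls type I error only for the primary and first secondary efficacy endpoints. That is correct, and it is why dilution of the estimate matters here more than loss of power.

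**Conclusion.** The point holds as a gap in attribution and tabulation. Relatedness is not split by agent, shared terms are ambiguous, and the OIT-induced events have no table or definition. The size for an overall count is moderate: a 20-point difference falls to between 10.5 and 17.75 points over the injection rates tried. This rests on the assumed 75%, the assumed injection rates and independence.

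Three stronger readings are tempting, and the documents do not support them.

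- *Injection reactions cancel the fall in OIT reactions, or the table hides an excess of injection events.* The SOC/PT rows keep injection-site and gastrointestinal terms apart, and an excess shows on its own row. Even an overall count would cancel only if 80% or more of the dupilumab arm had injection-related events, on the rates above.
- *Power collapses.* Starting from the 40% gastrointestinal rate in section 1.1, halved to 20%, with injection rates of 5% and 15%, the pooled rates are 43% and 32% and power falls from 66% to 23%. The arithmetic is correct, but it merges a gastrointestinal-only rate with injection events, which no listed table does. From the 95% all-related rate, with 75% assumed under dupilumab and the same injection rates, power goes from 89% to 79%.
- *The trial is designed to show fewer OIT reactions.* That is part of the hypothesis and a secondary safety objective; the powered endpoint is the week 18 food challenge.

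**What to change.** 1. On the AE form, record relatedness separately for milk OIT and for dupilumab/placebo, as the sample SAE form allows, and say so in section 11.3.2.
2. In section 13.6.1, replace the single relatedness bullet with two tables by arm, by SOC and PT: AEs related to milk OIT, and AEs related to the injection. An event possibly related to both appears in both.
3. In section 3.5.2, define OIT-induced as judged related to milk OIT.
4. Add a by-arm table of the dosing reactions recorded under section 11.2.1, split by agent, and include the milk ones in the OIT safety comparison. Without this step, the milk-related AE table would omit expected milk reactions within two hours of dosing, apart from the home-dosing exceptions.

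The cost is one extra form field per agent, if the routine form lacks it, a few more tables, and some double-listing of events attributed to both agents. The primary analysis and sample size are unaffected. Step 1 should come first, since attribution cannot be reliably recovered later.

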13.7. Additional Statistical Data Handling Conventions

The following analysis and data conventions will be followed:

Definition of baseline:

- The baseline assessment will be the latest, valid pre-first-dose assessment available

General rules for handling missing data (for assessments other than efficacy):

- If the start date of an AE or concomitant medication is incomplete or missing, it will be assumed to have occurred on or after the intake of study medication, except if an incomplete date (e.g. month and year) clearly indicates that the event started prior to treatment. If the partial date indicates the same month or year of the intake of study medication date, then the start date by the study medication intake date will be imputed; otherwise, the missing day or month by the first day or the first month will be imputed.
- No imputations for missing laboratory data, vital sign data, or physical examination data will be made.

Unscheduled assessments:

- Extra assessments (laboratory data or vital signs associated with nonprotocol clinical visits or obtained in the course of investigating or managing AEs) will be included in listings, but not summaries. If more than 1 laboratory value is available for a given visit, the first observation will be used in summaries and all observations will be presented in listings.

Statistical considerations surrounding the premature termination of a study:

- If the study is terminated prematurely, only those parameters required for reporting to regulatory authorities will be summarized.

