3. STUDY DESIGN

3.1. Study Description and Duration

This is a phase 2, multicenter, randomized, double-blind, placebo-controlled, 2-arm study in approximately 116 subjects aged 4 to 50 years, inclusive, who are allergic to cow's milk. The study consists of a screening period and a 24-week treatment period, which includes a 4-week run-in period with dupilumab or placebo followed by 12 weeks of treatment with dupilumab or placebo in combination with a gradual up-dosing of milk protein OIT, then followed by 8 weeks of milk OIT dosing with no dupilumab or placebo (Figure 1). The duration of the study is approximately 24 weeks, excluding the screening period.

Figure 1. Study Design of the Phase 2 Study to Test the Efficacy Dupilumab as an Adjunct to Milk OIT

Screening

After obtaining informed consent/assent, subjects will be assessed for eligibility at a screening visit. Procedures for the screening visit may be spread over the course of one to three days; these days do not need to be consecutive and can be spread out over the course of the entire screening window. During screening visits, subjects will be evaluated for the study eligibility criteria.

During screening visits, subjects will undergo double-blind, placebo-controlled, food challenges (DBPCFCs) to confirm milk allergy. The active challenge will consist of 6 doses of milk protein given every 15 to 30 minutes in increasing amounts up to a cumulative total of 444 mg of milk protein. The doses will be 1, 3, 10, 30, 100, and 300 mg. The placebo challenge will consist of placebo material (oat) also given in 6 doses matching that of the active challenge. Both milk protein and oat will be concealed in an age-appropriate, non-offensive food vehicle that aids in masking the taste and appearance.

Before each challenge, the subject will have a physical assessment by a trained clinician of the study team who is blinded to the testing material. All food challenges will be performed under clinician supervision. If the study team suspects a reaction may be developing, they may exercise their clinical judgment to separate doses by up to an additional 30 minutes (1 hour maximum between doses).

Reactions will be scored using the Common Terminology Criteria for Adverse Events (CTCAE) Version 5.0. The food challenge will be stopped and appropriately treated when the clinician finds

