At week 4 (Visit 4), participants will return to clinic undergo an initial dose escalation to determine the dose in which they will begin daily milk protein OIT. As detailed above, the subject will have a physical examination and lung function assessment conducted to ensure it is safe and appropriate to proceed with the escalation. Prior to the first dose of study drug at Visit 4, participants will undergo blood draw. Dupilumab/placebo will be administered in clinic at least 30 minutes prior to the first dose of milk OIT. Vital signs will be taken prior to dupilumab/placebo dosing, and again prior to the start of the initial dose escalation.

The initial dose escalation will consist of three doses of milk protein given every 15 to 30 minutes in increasing amounts up to a cumulative total of 35 mg milk protein. The doses will be 5, 10, and 20 mg protein mixed in an age-appropriate, non-offensive food vehicle (**Table 3**). The escalation may be stopped at the occurrence of any AE per clinician discretion. Participants unable to tolerate 5 mg milk protein during the initial dose escalation will be considered treatment failures.

Table 3. Initial Dose Escalation Regiment

Dose #	Milk OIT Dose (mg protein)
1	5
2	10
3	20

Each participant will be monitored for a minimum of 2 hours following the last dose administered and discharged from the clinic only when deemed clinically stable by a study clinician. Participants will be discharged with a two-week supply of milk OIT doses for daily home-dosing at the highest non-cumulative dose tolerated (i.e. 5, 10, or 20 mg protein) during escalation. The first dose will be taken at home the day after Visit 4, and the participant will return to clinic in two weeks, plus or minus 5 days, to attempt to escalate their daily dose according to **Table 1**. Daily Dosing & Symptom Diary and epinephrine auto-injector training will be repeated prior to discharge.

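### The partial-date rule in section 13.7 can overwrite a known month and re-date milk-phase events to the first dose, because its year test is not limited to dates whose month is unknown

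*Combined protocol and SAP*

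**What the plan says.** Section 13.7 covers incomplete start dates of AEs and concomitant medications. It works in three steps.

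- An incomplete date is assumed to fall on or after study-medication intake, "except if an incomplete date (e.g. month and year) clearly indicates that the event started prior to treatment".
- The next sentence sets a condition, "If the partial date indicates the same month or year of the intake of study medication date", and its consequence, "then the start date by the study medication intake date will be imputed".
- Every other partial date gets a default: "otherwise, the missing day or month by the first day or the first month will be imputed".

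The first step carves out dates clearly before treatment. No step carves out a recorded month that is clearly after the first dose. The rule also does not say which intake is meant. I read it as the first dose of dupilumab or placebo (Visit 2, week 0).

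One secondary safety objective in section 2.3 depends on when an event began: "To compare the safety of each treatment cohort as measured by rate and severity of allergic and non-allergic AEs during respective study phases". Section 13.6.1, however, defines only a pretreatment period and a single treatment period, and lists no summary by phase.

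**The concern.** The condition joins month and year with an or, and it does not depend on which part of the date is missing. If the day alone is missing, the month is known and usable. Yet a match on the year is enough to discard that month and substitute the first-dose date.

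This trial is sensitive to that substitution because the first four weeks contain no milk. An event that began in the second or third month of milk dosing would appear on the first injection day, in a phase when no oral immunotherapy reaction could occur. Two programmers reading the same sentence could also produce different onset dates, and so different by-phase tables. The same sentence governs concomitant medications, so a short course with a known stop date could appear to have started months earlier than it did.

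**Working it through.** The plan gives no figure on this point, so there is nothing to reproduce. The check applies the rule by date arithmetic.

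**Inputs from the documents**

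- Run-in without milk, section 3.1: "a 4-week run-in period with dupilumab or placebo followed by 12 weeks of treatment".
- Start of milk, section 8.3: "At week 4 (Visit 4), participants will return to clinic undergo an initial dose escalation". This is taken as 28 days after first dose.
- Length of follow-up, section 3.1: "The duration of the study is approximately 24 weeks, excluding the screening period". This is 24 × 7 = 168 days.

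**Assumptions (not in the documents)**

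- First-dose dates are uniform over the calendar years 2022 to 2025 (1,461 days).
- Onset is uniform over days 28 to 168 after first dose (141 days).
- Month and year are recorded; the day is missing.

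**Worked examples (assumed dates)**

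1. First dose 10 January 2022, so milk starts 7 February 2022. The AE is recorded as April 2022. The year matches, so the literal rule gives 10 January 2022, inside the run-in. Comparing month and year together gives no match, so the date becomes 1 April 2022. That is 21 + 28 + 31 + 1 = 81 days after first dose, in the milk phase.
2. First dose 10 November 2022, AE recorded as January 2023. Neither month nor year matches, so the literal rule itself gives 1 January 2023. The recorded month survives here only because the year has turned.

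**Share moved to the first-dose date, literal reading**

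An onset t days after first dose falls in the next calendar year for t of the possible first-dose dates in each year. With an average year of 1,461/4 = 365.25 days, the share in the same year is 1 − t/365.25. Within 168 days the same month name cannot recur in a different year, so the month test adds nothing. Averaging over a window replaces t by its midpoint:

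| Onset window (days) | Midpoint | Share moved |
|---|---|---|
| 28–168 | 98 | 1 − 98/365.25 = 73.2% |
| 28–112 | 70 | 1 − 70/365.25 = 80.8% |
| 112–168 | 140 | 1 − 140/365.25 = 61.7% |

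Full enumeration of every first-dose date and onset day gives the same three figures.

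The share depends heavily on the date of first dosing. For days 28 to 168 it is 100% for a first dose on 10 January, 1 June or 15 July 2024. For 1 October 2024 it is 64/141 = 45%, and for 10 December 2024 it is 0%.

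**Effect of matching the test to what is known (enumeration, days 28–168)**

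| Reading | Moved to first dose | Imputed date falls in run-in |
|---|---|---|
| Literal | 73.2% | 74.1% |
| Month and year compared together | 0.1% | 10.4% |

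The residual 10.4% comes almost entirely from the first-of-month default. It is 17.3% for onsets on days 28 to 112 and zero for days 112 to 168.

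**The case against.** The strongest reply is that the sentence was meant item by item. Its closing words, "otherwise, the missing day or month by the first day or the first month will be imputed", make sense only if day is paired with first day and month with first month. On the same pairing, the condition would use the month when the day is missing and the year when the month is missing. That is probably the intent, but the text does not state it. So the percentages describe a literal reading, not the most likely coding.

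The exposed set should also be small:

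- Section 11.2.1 records expected, related symptoms within two hours of dosing as dosing reactions rather than AEs, apart from home-dosing episodes that are Grade 3 or higher or serious.
- Daily diaries (section 6.3), diary review at two-weekly visits (section 8.3) and data entry within 10 days (section 14.2) make a missing day unlikely.

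This stands, and it limits the size of the problem.

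Three larger consequences might be inferred, and the documents support none of them.

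- *Screening events become treatment-emergent.* A recorded month and year clearly before first dose is the very case that the exception in the same bullet names. The sentence that follows does not repeat the exception, so it is worth stating that it takes precedence.
- *Attribution shifts from milk to dupilumab.* Section 11.3.2 leaves attribution to the investigator on all available information, with final determination for safety reporting by the sponsor. An analysis-stage date does not alter it.
- *The AE tables are distorted.* A moved milk-phase event stays in the same arm and the same single treatment period. The section 13.6.1 summaries (by system organ class and preferred term, severity, relationship, and events of special interest) are unchanged.

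**Conclusion.** The wording defect is real and its impact is low. As written, the rule can replace a known later month with the first-dose date. The 73% is a worst case that rests on the literal reading, uniform first-dose and onset dates, and intake meaning first dose. It is a share of month-known, day-missing onsets on days 28 to 168, not of all AEs. The number of such records is not given, so the effect on any table cannot be sized.

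The consequence is limited to onset date and study phase, and to concomitant-medication start dates. It bears on the by-phase safety objective once a by-phase table is produced. Nothing here touches the primary efficacy result.

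**What to change.** Replace the two imputation clauses with wording that matches the test to the missing part:

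> If only the day is missing and the month and year equal those of the first dose, impute the first-dose date; if only the day is missing and the month or year differs, impute the first of the recorded month. If day and month are missing and the year equals that of the first dose, impute the first-dose date; otherwise impute 1 January. The exception for dates clearly before treatment takes precedence.

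This does not by itself protect phase assignment. About 10% of month-known onsets on days 28 to 168 would still land in the run-in through the first-of-month default, and year-only dates in the first-dose year still go to the first dose. Any by-phase table should therefore assign phase from the recorded month and the participant's milk start date, not from the imputed day. It should also say how a month that contains the milk start is handled.

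The cost is a few lines of SAP text and a small change to derivation code, with no downside. The opening of section 13 says the final SAP is issued before the database is locked and unblinded, so the change can be made blind.
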